7.5. Listing of Subject Inclusion and Exclusion Criteria

For screen failures, a listing for all subjects will be provided showing which specific eligibility criteria were not met.

7.6. Medical History and Medical Conditions Present at Entry

The medical history (captured on the eCRF) will be coded using version 20.1 or later of the Medical Dictionary for Regulatory Activities (MedDRA) into system organ class and preferred term. The frequency of subjects with medical history by system organ class and preferred term will be presented on the safety population.

7.7. Handling the Use of Assistive Device During the 6MWT

Subjects using a permitted assistive device during the Screening/Baseline 6MWT should use the same assistive device for all follow-up 6MWT assessments in the study. If the subject added a new device, changed the device at certain visits, or did not use the assistive device, then that will be considered a protocol deviation as the change can affect the primary endpoint and the results of these assessments. See Section 6.1.6 and Section 6.4 for the listing of pre-defined major protocol deviations and the listing of intercurrent events.

7.8. Prior and Concomitant Medications and Nondrug Therapies

Prior medications and nondrug therapies are defined as any medication or nondrug therapy taken or occurring before the first dose of study drug. Concomitant medications and nondrug therapies include medications and nondrug therapies with start dates (and times) on or after the first dose of study drug, medications and nondrug therapies with onset dates (and times) prior to the first dose of study drug without a stop date, or medications and nondrug therapies with a stop date (time) after the first dose of study drug. Medications starting after the last dose of study drug will not be considered as concomitant but will be flagged as post medications in the listing of medications. Nondrug therapies include physiotherapy and occupational therapy, procedures, surgery, or use of assistive devices.

Prior and concomitant medications are coded to indication-specific Anatomical Therapeutic Chemical classification (ATC) and preferred name using the World Health Organization Drug Dictionary (WHO DDE, September 2013 or later).

Prior and concomitant medication use will be summarized by level 4 ATC and preferred name using the number and percentage of subjects by treatment group. Medications will be sorted alphabetically by ATC and preferred name within ATC, and in decreasing order of the total number of subjects who took each medication within each ATC class. Subjects with multiple occurrences of a medication in ATC and preferred name will only be counted once within each ATC and preferred name. In addition, the total number of subjects to ever take any concomitant medications will be presented. Since medications are coded to ATC by indication, preferred names may appear under multiple ATCs.

A listing of all medications, both prior to infusions and concomitant, and nondrug therapies will be presented. Investigator verbatim descriptions as well as coded terms will be included in the listings. Any abbreviations and codes will be clearly explained on each page of the listing. The listing will be sorted by treatment group and subject identifier, and will include level 4 ATC,

preferred name, reported name, dose, route of administration, dosing frequency, start date, end date, indication, and period of medication (prior only, concomitant only, prior and concomitant), and nondrug therapy. Pre-medications (which are a subset of all medications) will be listed in a separate data listing, and this listing will include a flag indicating whether the specified medication is a new pre-medication and whether there were changes in the subject's pre-medication (eg, changed to a different pre-medication change in dose of the pre-medication) prior to infusions.

Prior and concomitant medications and nondrug therapies will be summarized by treatment group.

7.8.1. Non-diagnosis Related Prior Medication History

Non-diagnosis related medications are medications taken for conditions other than the one under study. These medications will be identified, and a supportive listing will be provided to include the unique data associated with the medication start and stop dates, whether the medication is ongoing, dose, frequency of administration, route of administration, trade name, generic name, and why it was prescribed.

7.8.2. Prior Diagnosis Related Medication History

Prior diagnosis related medication history, if available, will be flagged in the listing discussed above in Section 7.8.1.

7.9. Baseline Physical Examination

Overall assessment of baseline physical exam (categorized as normal, abnormal, or not performed) will be summarized by number and percent, together with post-baseline data.

7.10. Baseline Vital Signs

Baseline vital signs including systolic and diastolic blood pressures (mmHg), heart rate (bpm), and body temperature (°C) will be summarized using descriptive statistics, together with post-baseline data.

7.11. Baseline Laboratory Data

Baseline laboratory results will be summarized with descriptive statistics, together with the post-baseline lab data. See Section 9.2 for analysis of clinical laboratory data.

7.12. Baseline Primary and Secondary Efficacy Evaluations

The results from the primary and secondary efficacy evaluations obtained at baseline will be summarized with appropriate descriptive statistics, together with post-baseline data.

8. ANALYSIS OF EFFICACY

8.1. General Considerations

The Statistical Analysis System (SAS[®]) software version 9.4 (or the latest version at the time of the analysis) and R software will be used for all statistical procedures and analyses.

In general, where basic summary statistics are needed, continuous variables will be summarized using descriptive statistics (n, mean, SD, median, Q1, Q3, minimum, and maximum); categorical variables will be summarized using number and percentage. For basic summaries involving the change from baseline, a 95% confidence interval (CI) for the mean difference will also be provided.

All inferential statistical tests for the primary and key secondary efficacy endpoints will be 1-sided and will be performed at the alpha level of 0.025, unless otherwise specified.

8.2. Testing Statistical Assumptions and Alternative Analysis

Estimated treatment effects such as the least squares (LS) means estimate from linear mixed models (eg, MMRM) and linear model (eg, ANCOVA) are known to be robust against moderate to high deviations from the normality assumption.

The underlying assumptions for the primary efficacy model will still be checked. The MMRM analysis will be used as the primary efficacy analysis for the 6MWD regardless of the results of the normality checks, as the MMRM model is believed to be robust against deviations from normality (Bartlett 2014). The nonparametric randomization-based covariance analysis described in Section 8.5.1.2 will be performed as a sensitivity analysis only if the normality assumption is notably violated with the Shapiro-Wilk test p-value < 0.01. The MMRM analysis assumes that data are missing at random (MAR). For this study, a lot of effort has been (and will continue to be) made to follow up all subjects so as to try to reduce the number of dropouts in the study. Despite all this, it is still possible to have subjects who could not do the 6MWD and/or FVC assessment due to COVID-19 related reasons. In view of the potential impact this can have on the efficacy assessments and analysis, the following analyses are considered:

- The MMRM analysis will be used as the primary efficacy analysis for the 6MWD, based on the ITT-OBS population.
The MMRM analysis uses all available data without imputation for missing data, and the amount of missing data for 6MWD at Week 52 is expected to be small (< 10%). Under these conditions, the MMRM is preferable to the ANCOVA (White, Carpenter et al. 2012; Siddiqui, Hung, et al. 2009).
- The ANCOVA model remains the main analysis for the % predicted FVC and other continuous endpoints, based on the ITT-LOCF population, unless otherwise specified.

The MMRM is a likelihood-based method that does not require a complete dataset; it uses all available data across visits, allowing it to account for differences in variability between visits; and it can model the within-subject variability. These features of the MMRM may be important now in view of the COVID-related interruptions at study sites resulting in delayed visits and make-up assessments, with potentially high between-visit variability. This can also be helpful

given that this study enrolled both ERT-naïve and ERT-experienced subjects who potentially differ in variability.

The validity of the MAR assumption in this study will be assessed by examining the amount and reason of the missing data and assessing whether they are balanced between the treatment groups. If the amount of missing data is small (eg, less than 10% of the total sample size), and/or are balanced between the treatment groups by reason of the missing data, then the impact of the missing data will be expected to be small.

In addition, a ‘control group imputation’ algorithm based on data sampled from the control group (alglucosidase alfa/placebo) will be implemented to replace missing data at the post-baseline visit. For example: For each instance of a missing 6MWD result at Week 52 in either treatment group (ie, active control or new treatment), a random sample of 15 values will be selected (with replacement) from the available set of data in the control group at Week 52. The average of these 15 values will then be used to replace the missing value. These steps will be carried out until all missing data at Week 52 have been replaced. The planned analysis (eg, MMRM) will then be performed on these newly imputed data. Consistency in the results with the original analysis (that is, the treatment effects are in the same direction, and the conclusions are similar) will suggest that the MAR assumption is valid.

8.3. Statement of the Null and Alternative Hypotheses

8.3.1. Primary Null and Alternative Hypotheses

The primary endpoint is the change from baseline to Week 52 in 6MWD, measured in meters. The primary endpoint analysis is based on a comparison of the change in 6MWD between ATB200/AT2221 (‘new treatment’) and alglucosidase alfa/placebo (‘control’).

H_0 : the new treatment is less effective than the control, with respect to the primary efficacy endpoint

H_A : the new treatment is more effective than the control, with respect to the primary efficacy endpoint

The primary null hypothesis will be tested at the 1-sided significance level of 0.025, unless otherwise stated.

8.3.2. Key Secondary Null and Alternative Hypotheses

There are 6 key secondary endpoints in hierarchical order of importance, as follows:

- Change from baseline to Week 52 in sitting FVC (% predicted)
- Change from baseline to Week 52 in the MMT score for the lower extremities
- Change from baseline to Week 26 in 6MWD
- Change from baseline to Week 52 in the total score for the PROMIS – Physical Function
- Change from baseline to Week 52 in the total score for the PROMIS – Fatigue
- Change from baseline to Week 52 in GSGC total score

The null and alternative hypotheses for superiority testing of all the key secondary endpoints are as follows:

H_{0i} : the new treatment is less effective than the control, with respect to the i^{th} key secondary efficacy endpoint

H_{Ai} : the new treatment is more effective than the control, with respect to the i^{th} key secondary efficacy endpoint

8.4. Multiple Comparisons and Multiplicity

The primary analysis is based on a single inter-group comparison of the primary efficacy endpoint between the new treatment and control at the 1-sided significance level of 0.025. The study has 6 key secondary efficacy endpoints which are ordered. The family-wise Type I error rate (FWER) for the statistical tests of the primary and key secondary endpoints will be controlled at 0.025. The p-value for comparing the primary and each key secondary endpoint will be calculated irrespective of its statistical significance.

To strongly control the FWER at this level, a gate-keeping approach will be utilized in which each family of statistical tests (family of primary and family of key secondary) will be conducted in a sequential manner. The test for the primary endpoint will be conducted first at the 0.025 significance level and, if significant, the ordered key secondary endpoints will be similarly tested at the 0.025 significance level. The statistical significance of the key secondary endpoints will be interpreted following a hierarchical testing order, each at the 1-sided alpha level of 0.025. If at any point the null hypothesis fails to be rejected, then that comparison and any other comparison below it cannot be claimed as successful.

The hypothesis tests included in the other secondary endpoints are not controlled, and each will be tested at the 1-sided alpha level of 0.025.

8.5. Analysis of the Primary Efficacy Endpoint

8.5.1. Primary Efficacy Analysis

The primary efficacy endpoint (change from baseline to Week 52 in 6MWD) will be analyzed using an MMRM model to compare between treatment and control on the ITT-OBS population.

For this analysis, the dependent variable is the change from baseline to all post-baseline visits. Independent variables in the model are the fixed, categorical effects of treatment, time (ie, visit), treatment-by-time interaction, ERT status, and gender, as well as the fixed, continuous covariates of baseline 6MWD, baseline age, baseline weight, and baseline height. SAS PROC MIXED will be used for the analysis, with restricted maximum likelihood estimation (REML) and unstructured within-subject covariance structure. The Kenward-Roger approximation will be used to estimate denominator degrees of freedom and adjust standard errors for the tests of fixed effects. If this model fails to converge, a compound symmetry (CS) covariance structure will be used instead. The OBSMARGINS (OM) option in the LSMEANS statement will be specified to allow for the use of the observed marginal distributions of the categorical variable rather than assuming a balance among the levels of the categorical variable. The E option will also be specified to check for estimability of LS means.

All the relevant estimates from this model, including LS means, standard errors (SE), treatment differences in LS means, and the corresponding 95% CIs will be estimated for each time point. The main variable to be estimated (ie, the estimand) in the primary comparison is the difference between ATB200/AT2221 and alglucosidase alfa/placebo in mean change in 6MWD from baseline to Week 52, regardless of whether intercurrent events have occurred. The significance test will be based on the treatment comparison of LS means at Week 52 and a p-value will be presented for this time point only. Estimated LS means (\pm SE) for the change from baseline by treatment group will be plotted over time.

Exploratory Interaction Tests:

The study is not powered to detect any interaction. However, the following interactions will be explored.

Time-based interactions (ie, time-by-baseline 6MWD, time-by-baseline age, time-by-baseline weight, time-by-ERT status) will be examined separately (one at a time) in separate MMRM models to understand the changes over time.

Similarly, treatment-by-covariate interactions (treatment-by-ERT status, treatment-by-baseline 6MWD, treatment-by-age, treatment-by-gender, treatment-by-weight, and treatment-by-height) will be explored. Each interaction term will be explored using a separate MMRM model that includes the full set of covariates of model terms (time, treatment-by-time interaction, gender, baseline 6MWD [continuous], baseline age [continuous], baseline weight [continuous], and baseline height [continuous]) as well as the added interaction term. The treatment-by-covariate interaction terms with a 2-sided $p < 0.10$ will be further examined clinically. Forest plots will be used to present the subgroups defined by the baseline covariates.

Secondary analyses of the primary endpoint and % predicted FVC (including supportive and sensitivity analyses) are described in Section 8.5.1.1 and Section 8.5.1.2. Analysis of the key secondary endpoints are described in Section 8.6, other secondary endpoints in Section 8.8, and subgroup analyses in Section 8.9. In all analyses involving the use of the LSMEANS, the OM option (as described above) will be used where applicable. If the LS means are not estimable with the OM option but they are without it, then the analysis without the OM option will be used. This will be footnoted accordingly.

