15.3.2.2. Missing Data Handling

Missing data may be imputed using methods of multivariate imputation by chained equations. Both missing-at-random and missing-not-at-random patterns will be considered and their impacts on robustness of the primary and/or key secondary analysis results will be assessed with a tipping point analysis. Further details of the approach will be provided in the full SAP.

Similarly, missing attributes for AEs will be imputed with the worst possible outcome, for summary purposes.

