6.3.2. Imputation for Missing Post-baseline Values

For this study, subjects who permanently discontinued the assigned study drug are subsequently discontinued from the study. However, these subjects are required to return for the EOS/ET visit. Efficacy assessments collected at the EOS/ET visit will be used to replace the missing endpoint value at Week 52 in the ITT-LOCF population. That is, the last available observation will be carried forward to replace the missing value at Week 52 (see Section 6.1.4.2).

The MMRM analysis is the primary analysis for the primary endpoint (6MWD), and it will be performed as an ITT-OBS (observed cases) analysis. That is, all available, observed values will be used without imputation, and missing data at Week 52 are not replaced.

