6.4. Handling of Intercurrent Events

Intercurrent events are defined as events that occur after treatment initiation and either preclude observation of the primary endpoint or affect its interpretation (eg, discontinuation of treatment, terminal events such as death, etc), per ICH E9 R1.

The potential intercurrent events for this study are listed in Table 5 together with the proposed strategy and handling of such events for the mixed-effect model repeated measures (MMRM) analysis and the analysis of covariance (ANCOVA).

Table 5: Accounting for Intercurrent Events

Intercurrent Event	Treatment Strategy for Handling Event	Handling of Event
Intervention for AEs, SAEs and IARs ^a ; Incorrect treatment assigned; Prespecified important major protocol deviations that can potentially affect the assessment of 6MWD.	Treatment policy strategy (based on ITT principle): 
 If subject continues in the study and dosing is resumed 	
For the ITT-OBS population: Value of interest (eg, 6MWD result observed at a given visit) will be used, regardless of whether the intercurrent event occurred. Note: No imputation will be performed for missing values at Week 52 (and other post-baseline visits). This is for the MMRM analysis.
 
For the ITT-LOCF population: Value of interest will be used, regardless of whether the intercurrent event occurred. Note: Missing values at Week 52 (and other post-baseline visits) will be imputed with the last available post-baseline assessment value. This is for the ANCOVA analysis.
 
Example: Compare “Treat A + Use of prohibited concomitant medication as needed” versus “Treat B + Use of prohibited concomitant medication as needed.”

	
 If subject permanently discontinues from study drug (and is withdrawn from the study) 	
For the ITT-OBS population: Observed value at time of discontinuation will be used. Note: No imputation will be performed for missing values at Week 52 and other post-baseline visits. Data after study discontinuation will be considered missing and will be handled by the MAR assumption in the MMRM analysis.
 
For the ITT-LOCF population: The last available assessment value will be used (regardless of whether the intercurrent event occurred). This setup is for the ANCOVA analysis.

Table 5: Accounting for Intercurrent Events (Continued)

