Intercurrent Event	Treatment Strategy for Handling Event	Handling of Event
Withdrawn at subject’s own request (eg, subject withdrew consent); Withdrawn based on investigator’s opinion; Withdrawn for persistent noncompliance ^b ; Withdrawn due to SAEs or COVID-19 related reasons. Withdrawn due to IARs	Treatment policy strategy (based on ITT principle) Here, subject is permanently discontinued from study drug (and is withdrawn from the study).	
For the ITT-OBS population: The observed value available at time of discontinuation will be used. No imputation will be performed for missing values at Week 52 and other post-baseline visits. Data after study discontinuation will be considered missing and will be handled by the MAR assumption in the MMRM analysis;
 
For the ITT-LOCF population: The last available assessment value will be used, regardless of whether the intercurrent event occurred.
 
Note: This setup is for the ANCOVA analysis.

Abbreviations: 6MWT = 6-minute walk test; AE = adverse event; IAR = infusion-associated reaction; ITT = intent-to-treat; MAR = missing at random

Note: A subject who permanently discontinues study drug is subsequently withdrawn from this study.

^a Intervention for AEs and IARs includes concomitant medications, dose modifications, interruptions, or withdrawal.

^b Withdrawn for persistent noncompliance with study drug, study requirements, or failure to return to the study site for infusion visits. Eg, subject missed 5 or more infusions; or subject’s calculated compliance value < 80%.

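### For subjects who stop study drug for good, the SAP states a treatment-policy estimand but the primary MMRM targets a hypothetical one, and the role of the early-termination 6MWD is contradictory.

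*SAP*

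**What the plan says.** **Target.** SAP 8.5.1 describes the estimand as the difference between arms "in mean change in 6MWD from baseline to Week 52, regardless of whether intercurrent events have occurred". SAP Table 5 (Section 6.4) names a treatment-policy strategy for every listed event, including permanent discontinuation and each reason for withdrawal.

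**What happens to subjects who stop.** SAP 6.3.2 states that "subjects who permanently discontinued the assigned study drug are subsequently discontinued from the study", and the note to Table 5 repeats it: "A subject who permanently discontinues study drug is subsequently withdrawn from this study". Protocol 12.2.6 asks them back for one Week 52/Early Termination visit. No efficacy visits are scheduled after that.

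**How the primary analysis treats them.** Table 5: "Data after study discontinuation will be considered missing and will be handled by the MAR assumption in the MMRM analysis". SAP 6.3.2 on the MMRM: "all available, observed values will be used without imputation, and missing data at Week 52 are not replaced".

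**Where treatment policy is carried out.** Table 5 has a separate branch, "If subject continues in the study and dosing is resumed", in which observed values are used whether or not the event occurred.

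**Sensitivity analyses.** Protocol 15.3.2.2 considers both missing-at-random and missing-not-at-random patterns and says that "their impacts on robustness of the primary and/or key secondary analysis results will be assessed with a tipping point analysis". SAP Table 7 lists no tipping-point analysis, and SAP Section 2 says that the final SAP supersedes the protocol's analyses. SAP 8.2 does include a control-group imputation. Each missing Week 52 value in either arm is replaced by the average of 15 values drawn from the observed control data, and the MMRM is rerun.

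**The concern.** A treatment-policy effect needs outcomes after the event, either observed or modelled as off-drug outcomes. For permanent stoppers this plan does neither. An MMRM under missing at random predicts their Week 52 result from subjects in the same arm with similar earlier values who remained in the study, nearly all still on drug. That matches treatment policy only if stopping makes no difference to later walking distance.

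The primary result would then be reported as holding regardless of discontinuation when it describes a setting in which nobody discontinued. If subjects who leave ATB200/AT2221 lose some of its added benefit, the reported figure is the more favourable of the two. SAP 4.5.1 already records early withdrawals related to COVID-19, so the event is not rare in principle.

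**Working it through.** **1. The plan's own figure.** Inputs from SAP 4.3: standardized effect 0.7, 66 and 33 evaluable subjects, one-sided 0.025 (equivalent to the protocol's two-sided 0.05), 10% dropout.
- Noncentrality = 0.7 × √(66 × 33 / 99) = 0.7 × √22 = 3.28, with 97 degrees of freedom. Exact t-test power is 0.902.
- 99 / 0.90 = 110 randomized.

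Both stated figures reproduce.

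**2. Size of the gap.** Let p be the share of the active arm that stops and r the share of added benefit kept at Week 52. Neither is given in the documents for off-drug subjects, so both are assumptions. SAP 4.3 plans for 10% dropout, and SAP 8.2 expects less than 10% missing 6MWD at Week 52.

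Treatment-policy effect = 0.7 × [1 − p(1 − r)]. Appendix 1 equates 0.7 SD with 20 to 40 m.

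| p | r | Effect (SD) | Gap (SD) | Gap (m) |
|---|---|---|---|---|
| 5% | 0 | 0.665 | 0.035 | 1 to 2 |
| 10% | 0 | 0.630 | 0.070 | 2 to 4 |
| 10% | 0.5 | 0.665 | 0.035 | 1 to 2 |
| 20% | 0 | 0.560 | 0.140 | 4 to 8 |

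**3. Power for the treatment-policy effect.** Stoppers count in this effect, so all 110 subjects (73 and 37) are in the sample. At p = 10%, r = 0, noncentrality = 0.63 × √(73 × 37 / 110) = 0.63 × 4.955 = 3.12, and exact power is 0.872. At p = 5% it is 0.904, and at p = 20% it is 0.785.

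**4. What the MMRM estimates.** A large-sample simulation used 400,000 subjects per arm and four visits. Assumed effects were 0.3, 0.5, 0.6 and 0.7 SD, with correlation 0.7 between visits. Both arms had the same dropout rate, active-arm benefit was fully lost after stopping, and the estimate was by likelihood with unstructured covariance. At 10% discontinuation:

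| Quantity | Random dropout | Dropout depending on last value |
|---|---|---|
| True treatment-policy effect | 0.628 | 0.629 |
| Missing-at-random estimate | 0.698 | 0.699 |
| Effect had everyone continued | 0.698 | 0.699 |
| Last on-drug value used as Week 52 | 0.675 | 0.675 |

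The planned estimate agrees with the had-all-continued effect, not the treatment-policy effect.

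**5. The early-termination 6MWD.** Three rules sit side by side.
- SAP 6.2.4 makes the average of the two tests at the Week 52/ET visit the final Week 52 value for analysis.
- SAP 6.3.2 describes that replacement for ITT-LOCF and leaves Week 52 unreplaced in the MMRM.
- Table 3 assigns only assessments after Day 316 to Week 52, so an earlier ET visit falls into the Week 12, 26 or 38 window.

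The last row of step 4 shows that the choice matters: using a last on-drug value as Week 52 gives 0.675, which is neither estimand.

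**The case against.** The strongest reply is that the mismatch is mostly one of labelling, with small consequences. Several parts of that stand.

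- **Scope.** Where the subject stays in the study and dosing resumes, observed values are used and treatment policy is carried out. The mismatch covers permanent discontinuation and withdrawal only.
- **Power.** A reader might infer that power drops to 83%, which is what an effect of 0.63 gives at 66/33. That counts dropout twice: 66/33 is already net of the 10%, and diluting the effect for the same subjects requires putting them back. With 110 followed the figure is about 87%.
- **Off-drug data.** A reader might infer that no off-drug information exists at all. Stoppers are asked back for an ET visit with two walk tests. Someone withdrawn after five consecutive missed two-weekly infusions (Protocol 9.3) is about 10 weeks past the last dose, so that value can be off-drug. It is still not a Week 52 outcome unless the visit happens to fall there, and the SAP does not say consistently how it enters the MMRM.
- **Sensitivity analysis.** A reader of Table 7 alone might think there is no control-based analysis. Section 8.2 has one, but it does not close the gap. It imputes once, ignores the subject's own earlier values, and uses a mean of 15 draws, whose SD is 1/√15 = 0.26 of a single value's, so variance is understated. It is presented as a check on missing at random rather than as an estimate of the treatment-policy effect.
- **Other analyses.** Table 7 row 2 refers back to the same Table 5 handling. The LOCF ANCOVA carries the last value forward and does not observe off-drug Week 52 outcomes.
- **Tipping point.** The SAP is entitled to supersede the protocol, so its absence is a gap in robustness rather than evidence of the mismatch.

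**Conclusion.** The point holds for permanent study-drug discontinuation and withdrawal: the SAP names treatment policy, and its primary MMRM essentially targets a hypothetical effect as if these subjects had continued. Calling it an on-treatment analysis would be wrong, because the model uses all randomized and dosed subjects and extrapolates for those who leave.

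The size is modest. It is 0.07 SD, or 2 to 4 m, at 10% discontinuation with all added benefit lost, and half that if half is kept. It would be larger if stoppers fell below control, and absent if stopping had no effect on later distance. These figures rest on assumed p and r, so the direction is conditional too. The documents do not support a claim that the sample size is wrong: 99 evaluable and 110 randomized both reproduce.

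The contradiction over the ET 6MWD stands on the text alone and needs no assumption.

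**What to change.** Before database lock:

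1. In SAP 8.5.1 and Table 5, label the MMRM estimand as hypothetical for permanent discontinuation and withdrawal, and as treatment policy only where the subject stays in the study.
2. Reconcile SAP 6.2.4, 6.3.2 and Table 3, so that one rule states whether and at which visit an ET 6MWD enters the MMRM.
3. In SAP 8.2, replace the single mean-of-15 imputation with reference-based multiple imputation (copy-reference or jump-to-reference, combined by Rubin's rules) as the sensitivity analysis aimed at treatment policy. Add the tipping-point analysis of Protocol 15.3.2.2 to Table 7.

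Following stoppers to Week 52 is the textbook remedy but looks out of reach here. SAP 4.4 describes randomization as done and 6.3.1 reports complete ITT baselines for 6MWD and FVC. Subjects discontinued because of COVID-19 may also enter the open-label study ATB200-07 (Protocol 8.1 and 13.3.3), where later values, including those of control subjects, would be on ATB200/AT2221.

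The cost is SAP wording, one or two sensitivity tables, and a supporting estimate that may be slightly less favourable.
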